## Study protocol

This study was approved by the Institutional Review Board at the Ohio State University and registered with clinicaltrials.gov (Registration number: NCT05961995). All participants signed an informed consent prior to this 6-week single-arm study.

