# Study outcomes

#### Primary outcomes

The primary outcomes were state and trait anxiety and mood states, measured using the State-Trait-Anxiety Inventory (STAI)(26) and Profile of Mood States (POMS) respectively.(27) The STAI has two 20-item subscales that measure the temporary emotional condition of "state anxiety" (STAI-S) and the long-standing personal characteristic of "trait anxiety" (STAI-T), respectively. The STAI-S evaluates amount of current feelings of apprehension, tension, nervousness, and worry. The POMS is a 35-item validated questionnaire that assesses mood across the 6 mood states of tension, depression, anger,

vigor, fatigue and confusion. These outcomes were measured immediately before and after a meditation session at baseline, at 3 weeks, and at the end of study (6 weeks).

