# Endocannabinoid concentrations and related lipids

Blood was collected for measurement of circulating endocannabinoid concentrations before and immediately after meditation sessions at baseline and at week 6 (first and last mediation sessions during the study). Serum concentrations of endocannabinoids *N*arachidonylethanolamine (AEA) and 2-arachidonoylglycerol (2-AG) and related lipids *N*oleoylethanolamine (OEA) and palmitoylethanolamide (PEA) were quantified by isotope dilution following measurement using atmospheric pressure, chemical ionization liquid chromatography/mass spectrometry (LC-APCI-MS).

Subjects completed the first and last meditation sessions at the clinical translational unit. These sessions were scheduled between 8 AM and 1 PM given diurnal variation in endocannabinoid concentrations. The remainder of the session were completed at home by subjects. All study questionnaires were completed at the beginning of the study (baseline), week 6 and 12.

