# **Statistical analysis**

Patient characteristics were summarized using means and standard deviations or medians and interquartile ranges for continuous variables, depending on the distribution of the data. Frequencies and relative frequencies were used to describe categorical patient characteristics. Changes in means for state and trait anxiety, mood states, health-related quality of life, daytime sleepiness, subscale scores and index scores of the BSI, and subscales scores of the COPE were examined over time (baseline, week 3, and week 6) using repeated measures ANOVA. Paired t-tests were used to compare means of state anxiety, total mood disturbance, visual analog scale scores, and levels of serum endocannabinoids and related lipids before and after HFM at baseline and before and after HFM at 6 weeks. Analyses were performed using SPSS version 28.0 (IBM SPSS, Armonk, NY). The level of significance for all analyses was  $\alpha$ =0.05.

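### Twelve tests of jointly primary outcomes, each at 0.05 with no ranking, adjustment or success rule: a claim of change that may rest on any one of them has a chance error well above 5%

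*Combined protocol and SAP*

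**What the plan says.** Under Primary outcomes, three constructs are named together and none is placed first: "The primary outcomes were state and trait anxiety and mood states". Mood is measured with the POMS, which "assesses mood across the 6 mood states of tension", depression, anger, vigor, fatigue and confusion. On timing: "These outcomes were measured immediately before and after a meditation session at baseline", and again at 3 and 6 weeks. Each visit therefore yields a before-session and an after-session score.

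Under Statistical analysis, two sets of tests fall on these outcomes:

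- Repeated measures ANOVA over baseline, week 3 and week 6: "Changes in means for state and trait anxiety, mood states" and several secondary scales.
- Before/after comparisons at the baseline session and at the 6-week session: "Paired t-tests were used to compare means of state anxiety, total mood disturbance", along with the VAS and the serum lipids.

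The section closes with a single threshold: "The level of significance for all analyses was" 0.05. The documents give no multiplicity adjustment, no order among the primary outcomes, no primary contrast and no rule for how many primary tests must succeed. They also do not say whether the before-session or the after-session score enters the ANOVA.

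**The concern.** When several outcomes are primary and the plan does not say which result, or how many, would support a conclusion, a report can rest on whichever primary test reaches p<0.05. The 5% threshold then controls the error of each single test, but not the error of the conclusion.

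Mood adds to the problem because it appears in two forms: as mood states in the ANOVA sentence and as total mood disturbance in the t-test sentence. State anxiety and mood are each tested both within a session and over time. What is at stake is whether a reported change in a primary outcome can be told apart from a chance finding among many tests.

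**Working it through.** The documents give no sample size, power or overall error to reproduce. The only stated input is 0.05 per test.

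**Step 1: count the primary tests.**

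- ANOVAs, literal reading: state anxiety + trait anxiety + six mood states = 8.
- Paired t-tests: (state anxiety, total mood disturbance) × (baseline session, 6-week session) = 2 × 2 = 4.
- Total: 8 + 4 = 12.
- If mood is collapsed to one POMS score in the ANOVA: 3 + 4 = 7.

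The secondary questionnaires, the VAS and the lipids are also tested at 0.05 and are not counted here.

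**Step 2: independent tests, nothing changes.** The chance of at least one p<0.05 is 1 − 0.95^k.

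- k = 12: 1 − 0.95^12 = 0.460.
- k = 7: 1 − 0.95^7 = 0.302.

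**Step 3: correlated tests.** Independence overstates the error, because the scales are related and total mood disturbance is presumably built from the six states. The planned ANOVAs and t-tests were therefore simulated with no true change. The assumptions, none of which is in the documents, were:

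- n = 30 and two-sided t-tests;
- a common correlation r across scales, all oriented the same way;
- within-person errors independent across occasions;
- total mood disturbance equal to the sum of the six states;
- before-session scores in the ANOVA.

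| r | 12 tests | 7 tests |
|---|---|---|
| 0.5 | about 36% | about 24% |
| 0.7 | about 30% | about 22% |
| 0.9 | about 21% | about 18% |

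Two variations, both at r = 0.5, set the upper ends. If before and after scores of a visit share half the within-person variance, 12 tests give about 37%. If POMS is drawn as one score instead of a sum, 7 tests give about 26%. The ranges are therefore about 21–37% and 18–26%.

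Sample size matters little. At r = 0.7, n = 20 gives 30.1% (12 tests) and 22.5% (7 tests), against 29.5% and 22.1% at n = 30.

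A cruder model, in which every pair of test statistics has the same correlation (including acute with over-time tests), gives lower figures: 23% and 18% at 0.7, and 13% and 11% at 0.9. These are still more than twice 5%.

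**Step 4: each aim taken alone.** In the simulation of Step 3, the four acute t-tests have an error of about 12–16% and the eight ANOVAs about 12–26%. Splitting by aim without adjustment does not bring either to 5%.

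**Step 5: power under Holm.** Take a paired t-test with a hypothetical 80% power at two-sided 0.05 and n = 30 (29 degrees of freedom). Its noncentrality is about 2.90. At the first Holm step its power is:

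- four tests (0.05/4 = 0.0125): about 60%;
- seven tests (0.05/7 = 0.0071): about 51%;
- twelve tests (0.05/12 = 0.0042): about 43%.

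**The case against.** Four arguments deserve weight.

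- **No any-one-test rule is stated.** The overall error applies to a claim that may rest on any single test, and the plan does not say that it will claim success that way. If every result is reported and claimed separately, each keeps its own 5%. This stands as a limit on how the figures are read. It does not remove the point: the outcomes are called primary, the Introduction sets efficacy as the objective with directional hypotheses, and nothing in the plan rules out a claim resting on one result.
- **The aims are separate questions.** The Introduction distinguishes an acute aim (1a, 1b) from a 6-week aim (2). The t-tests fit the first and the ANOVAs the second, so two families are as defensible as one. This stands and shapes the fix, but the plan adjusts within neither.
- **The sizes depend on assumptions.** This also stands. The documents support no particular correlation or n, so only a range is fair.
- **The design is the larger limit.** Participants enrolled "prior to this 6-week single-arm study". Repeated questionnaires, rest or regression to the mean could move scores without any effect of meditation, and adjustment does not address that. True, but it is a separate limitation.

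A reader might infer stronger versions. One is that there are 13 tests and a 49% error (1 − 0.95^13 = 0.487). That needs total mood disturbance to enter the ANOVA, and the plan names it only for the t-tests. Another is that nearly half of null studies run this way would report a positive result. The 46% requires independent tests and an any-one-test claim, and the documents establish neither. A third is that adjustment would let the study support efficacy. Without a control group it would not.

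**Conclusion.** The concern holds in this form: 12 primary tests on the literal reading (7 if mood is one score), all at 0.05, with nothing in the plan to control the error of a claim resting on any one of them. If nothing changes, that error is 46% or 30% under independence. It is about 21–37% or 18–26% in simulations with an assumed n of 30 and correlations of 0.5 to 0.9. The test counts come from the text; the simulated sizes are illustrations. The direction does not depend on them, since every structure tried stays at more than twice 5%.

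The point concerns claims of change only. It should be corrected, and the correction is cheap, but it is not the main limit on what a single-arm study can show.

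**What to change.** In the Statistical analysis section:

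1. Apply Holm at 0.05 to the primary tests as already defined, and report raw and adjusted p-values for all of them. Use either one family of 12, or two families that follow the aims: acute (4 paired t-tests) and 6-week (8 ANOVAs). With two families, make each aim's claim separately and state that the error across both can reach 0.05 + 0.05 = 10%.
2. Claim change only where the adjusted p is below 0.05, and call it change, not efficacy.
3. State whether the before-session or the after-session score enters the ANOVA. If both are analysed, the family grows.
4. Reducing mood to total mood disturbance (7 tests) is an option only if it is disclosed as a change to the primary outcome.
5. Report secondary outcomes and lipids as exploratory.
6. The section is written in the past tense. If results are already known, label the adjustment post hoc.

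The cost is no new data but lower power: a hypothetical 80% falls to about 60%, 51% or 43% at the first Holm step of four, seven or twelve. Later steps are less strict.

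A separate matter affects which tests exist. The endocannabinoid section says "All study questionnaires were completed at the beginning of the study (baseline), week 6 and 12", while the outcome and analysis sections use baseline, week 3 and week 6. These must be reconciled.
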